		██████████ will be emphasized using the 1.0 increment scale for internal purposes only.	
1.11	Iris Color	The investigator will record the subject's iris color based on the scale provided.	Appendix E
1.12	Subjective Refraction	The investigator will complete a subjective refraction (sphere and cylinder) and record the resultant distance visual acuity OD, OS, and OU to the nearest letter. Best corrected distance visual acuity (BVA) must be 20/25+3 or better in each eye.	██████████
1.13	Eligibility after Baseline	All responses to Inclusion Criteria questions must be answered "yes" and all responses to Exclusion Criteria questions must be answered "no" for the subject to be considered eligible.	
1.14	Eye Rinse	The study coordinator, investigator, or technician will rinse the subject's eyes thoroughly with saline.	

Visit 1: Treatment 1 Lens Fitting			
Step	Procedure	Details	
1.15	Lens Selection	Assign the study lens based on the randomization scheme. Select the contact lens power based on subjective refraction.	
1.16	Lens Insertion	The Investigator or the subject inserts the study lenses. Record the time of lens insertion. Check for lens damage under the slit lamp before proceeding with lens settling. Replace damaged lenses if applicable.	
1.17	Lens Settling	Allow the study lenses to settle for a minimum of 5 minutes.	
1.18	Spherical Over Refraction and Modification	Perform a spherical over-refraction OD and OS. Optimize the lens power to achieve an over-refraction of ± 0.00 D OD and OS.	

Visit 1: Treatment 1 Lens Fitting			
Step	Procedure	Details	
		Ensure that any new lenses are not damaged. One modification attempt will be allowed.	
1.19	Time Interval	Please wait for at least 10 minutes from final lens insertion to continue.	
1.20	Subject Reported Ocular Symptoms	Subjects will respond to a verbal open-ended symptoms questionnaire.	
1.21	Visual Acuity	Record the distance Snellen visual acuity with the contact lenses (OD, OS, and OU) to the nearest letter. Smaller lines must be shown until the subject incorrectly identifies at least 50% of the letters.	
1.22	Subjective Lens Fit Assessment	
Subjective Assessment of the Lens Fit. If the fit is graded as unacceptable based on the criteria below, then the subject is discontinued from the study and will not be replaced.
 
 1. Limbal exposure in any gaze 2. Edge lift 3. Insufficient and/or excessive movement in all three movement categories 	

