2.5.	Follow-Up Questionnaire	Subjects will respond to the following questionnaires: 1. CLUE Follow-up 2. GSI Product Performance	
2.6.	Visual Acuity	Record the distance Snellen visual acuity with the contact lenses (OD, OS, and OU) to the nearest letter. Subjects must read the smallest line until at least 50% of the letters are read incorrectly.	
2.7.	Quick Contrast Sensitivity	████████ only. Perform the 4 m contrast sensitivity test once OD and OS using the 25-item methodology while wearing the study lenses.	
2.8.	logMAR (ETDRS) Visual Acuity	Perform 4 m distance ETDRS LogMAR visual acuity test OD and OS under the following conditions: 1. Bright room illumination / low contrast charts a. Room illumination >400 lux b. Chart luminance 120-200 cd/m ² c. One low contrast chart per eye. 1) OD: chart LC-1 2) OS: chart LC-2 2. Low room illumination / high contrast charts a. Room illumination <2.5 lux b. Chart luminance 2.0-5.0 cd/m ² c. One high contrast chart per eye. 1) OD: chart HC-1 2) OS: chart HC-2	████████ ████████
2.9.	Subjective Lens Fit Assessment	Subjective Assessment of the Lens Fit. If the fit is graded as unacceptable based on the criteria below, then the subject is discontinued from the study and will not be replaced. 1. Limbal exposure in any gaze 2. Edge lift 3. Insufficient and/or excessive movement in all three movement categories	

Visit 2: Treatment 1 Follow-Up			
Step	Procedure	Details	
2.10.	Surface Deposits	Record any front and back surface lens deposits.	
2.11.	Lens Removal & Storage	Both lenses will be removed and stored wet in a labeled container with Opti-Free® PureMoist®. The lenses can be stored refrigerated or frozen prior to shipment back to the Sponsor. Lenses will be stored at JJVC for 45 days after LSLV for laboratory testing (Section 7.4).	
2.12.	Slit Lamp Findings	
Slit Lamp Classification Scale [REDACTED] will be used to grade the findings. Record only whole numbers. Limbal and Bulbar Conjunctival Hyperemia findings [REDACTED] [REDACTED] and Corneal Staining Assessment [REDACTED] [REDACTED] will be emphasized using a more detailed scale.
 
Note: Findings must be grade 2 or less as graded on the FDA scale [REDACTED] to continue onto Trial Period 2. If the subject is not eligible, they must be followed as an adverse event. Once resolved, the subject is terminated from the study. Adverse events must be reported to the JJVC monitors immediately.
	[REDACTED] [REDACTED] [REDACTED]

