Acceptable lens fit will be assessed for each subject eye at all scheduled study visits (fitting [visit 1] and follow-up [visit 2]). Fit acceptance rate will be based on the lens fit acceptance of eyes wearing the Test lens only. Fit rates of the Control lens will also be collected but are not a primary endpoint.

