5. STATISTICAL HYPOTHESES FOR STUDY OBJECTIVES

5.1. Primary Hypotheses

All primary hypotheses must be met in order to satisfy the primary objective of this study.

1. The Test lens will be non-inferior to the Control lens with respect to Distance Monocular logMAR Visual Acuity at the two-week follow-up evaluation under both lighting conditions (Bright illumination low contrast and dim illumination high contrast). A non-inferiority margin of 0.05 logMAR will be used.

2. The Test lens will be non-inferior to the Control lens with respect to the percentage of eyes with Grade 3 or higher Slit Lamp Findings (Biomicroscopy) across all follow-up visits (scheduled and unscheduled). A non-inferiority odds ratio margin of 2 will be used.
3. The proportion of eyes with acceptable fit will be greater than 90% across all visits (scheduled and unscheduled) for all subjects wearing the Test lens.
4. The Test lens will be non-inferior to the Control lens with respect to CLUE Overall Comfort at the two-week follow-up evaluation. A non-inferiority margin of -5 points will be used.
5. The Test lens will be non-inferior to the Control lens with respect to Vision satisfaction in bright lighting at the two-week follow-up evaluation. A non-inferiority cumulative odds ratio margin of 0.67 will be used.

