visual performance was analyzed using a linear mixed model. Lens type was included as the only fixed effect. A compound symmetric (CS) covariance matrix was used to model the correlation between measurements on the same subject across study periods. Below is the variance-covariance matrix used in the visual performance model.

$$\sum_{\text{visual performance}} \begin{pmatrix} 0.003518 & 0.000374 & 0.000374 \\ 0.000374 & 0.003518 & 0.000374 \\ 0.000374 & 0.000374 & 0.003518 \end{pmatrix}$$

Acceptable Lens Fit

Acceptable lens fit is a binary response as $y=1$ if a subject eye has an acceptable fit and $y=0$ otherwise. Indicated by the historical data there was only 1 observed unacceptable lens fittings for the Test lens therefore, the common reference rate of 95% was selected for the sample size calculation, since this is considered to be a more conservative reference proportion. Assuming a correlation 0.80 between measurements within the same subject and period (intra-eye correlation); and assuming a correlation of 0.50 between measurements within the same subject across periods. A total of 2000 replicating trials were simulated to estimate a sample size with a minimum statistical power of 80%.

Slit Lamp Findings

There were no Grade 3 or higher SLFs observed in any of the historical studies. Assuming no difference between study lenses and a correlation 0.80 between left and right eyes within the same subject and period; and a correlation of 0.50 between measurements within the same subject across periods (intra-subject correlation). A reference rate of no more than 5% was assumed (worse-case scenario) with a non-inferiority odds ratio margin of 2. A total of 2000 replicating trials were simulated, each replicated sample was analyzed using a generalized estimating equation (GEE) model with a binary distribution and the logit as the link function. Each model included lens type as the only fixed, eye was included as a random effect. The Odds ratio and corresponding 95% confidence interval was used estimate differences between the Test and Control lenses. The upper limit of each 95% confidence interval was compared to 2; if the upper limit was below 2 then NI=1; otherwise NI=0. Statistical power was calculated at the average NI. A sample size of 50 was chosen to achieve a minimum statistical power of 80%.

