Independent vague $N(0, 1000)$ priors for the regression coefficients β_i $i=1, \dots, 5$. For θ_n , we are considering the following priors

$$\begin{aligned}\pi_0(\theta_1) &\sim N(0, 100) \\ \pi_0(\theta_2 | \theta_1) &\sim N(0, 100) I(\theta > \theta_1) \\ \pi_0(\theta_3 | \theta_2) &\sim N(0, 100) I(\theta > \theta_2) \\ \pi_0(\theta_4 | \theta_3) &\sim N(0, 100) I(\theta > \theta_3)\end{aligned}$$

For the variance of random effects independent vague normal priors will also be used; $\sigma_p^2 \sim \text{inverse-gamma}(0.001, 0.001)$ and $\sigma_s^2 \sim \text{inverse-gamma}(0.001, 0.001)$. The Metropolis sample algorithm as implemented in the SAS/Stat MCMC Procedure will be used to estimate the posterior distributions of the unknown parameters. Inferences will be made based on the posterior credible interval for the relevant parameters.

Hypothesis Testing

The null and alternative hypotheses for superiority are as follows:

$$\begin{aligned}H_0 \quad OR &\leq 0.67 \\ H_A \quad OR &> 0.67\end{aligned}$$

Where OR represent the cumulative odds ratio of having higher rating of the Test lens compared to the Control lens. Non-inferiority will be declared if the lower bound of the 2-sided 95% credible confidence interval is above 0.67, i.e. $P(OR=e^{\beta_1} > 0.67 | y) = 0.975$.

Primary Safety Analysis:

Lens Fit Acceptance

Lens fit acceptance will be analyzed using a Bayesian Logistic regression random-effects model to estimate the proportion of subjects' eyes wearing the Test lens having acceptable lens fitting. The regression model will include period, sequence of lens wear and first order carryover effect as fixed effects. Site and subject will be included in the model as random effects.

Let $y_{ijklm}=1$ if an acceptable lens fit is observed for eyes wearing the Test lens only and $y_{ijklm}=0$ otherwise for the m^{th} subject, from the l^{th} site, for the i^{th} eye in the j^{th} period using the k^{th} sequence.

$$y_{ijklm} \sim \text{Binary} (p_{ijklm})$$

$$p_{ijklm} = \frac{\exp(\mu_{ijklm})}{1 + \exp(\mu_{ijklm})}$$

$$\mu_{ijklm} = \beta_0 + \beta_1 \text{Lens}_{i[j,k]} + \beta_3 \text{period}_{j1} + \beta_4 \text{period}_{j2} + \beta_5 \text{sequence}_k + \beta_6 \text{Carry1}_{i[j,k]} + \gamma_1 + \delta_{m(l)} + \alpha_{j(m(l))}$$

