We assume the random subject eye effects are i.i.d as $\alpha_{j(m(l))} \sim N(0, \sigma_{eye}^2)$ for eye nested within subject within clinical site, the random effect for subject are i.i.d as $\delta_{m(l)} \sim N(0, \sigma_{subject}^2)$ for subject nested within clinical site and the random clinical site effects are i.i.d as $\gamma_m \sim N(0, \sigma_{site}^2)$ for i=1, 2 (eye) , j=1, 2, 3 (period) k=1, 2 (Sequence) l=1, ...6 (Site) m=1, ...n_l(subject/site).

For the β coefficients, independent non-informative priors $N(0, 10000)$ will be used. For the variance of random effects of $\sigma_{eye}^2, \sigma_{subject}^2$ and σ_{site}^2 , independent non-informative conjugate priors inverse-gamma (0.001, 0.001) will be used. The Metropolis-Hastings algorithm as implemented in the SAS/STAT 14.2 PROC MCMC procedure will be used to estimate posterior distributions of the unknown parameters. Inferences will be made based on the posterior credible interval for the relevant parameters.

Hypothesis Testing

With respect to acceptable lens fit the null and alternative hypothesis for superiority is as follows:

$$\begin{aligned} H_0 &= p \leq 0.90 \\ H_1 &= p > 0.90 \end{aligned}$$

Where, p represents the proportion of subject eyes that achieve acceptable fit for the Test lens.

Where p is calculated as:

$$p = \frac{\exp(\mu)}{1 + \exp(\mu)}$$

$$\text{And } \mu = \beta_0 + \beta_1 + \frac{\beta_3}{3} + \frac{\beta_4}{3} + \frac{\beta_5}{2} + \frac{\beta_6}{2}$$

Success for acceptable fit will be declared if the lower bound of the 2-sided 95% credible interval of the proportion is greater than 0.90; i.e. $P(p > 0.90) \geq .975$.

If the full planned model fails to converge, reduced versions may be considered.

Primary safety analysis:

Slit Lamp Findings

Grade 3 or higher slit lamp findings will be analyzed using a Bayesian Logistic regression random-effects model to compare the Test and Control lenses. The regression model will include baseline slit lamp findings, lens type, period, sequence of lens wear and first order carryover effect. Site and subject will be included in the model as random effects.

Let $y_{ijklmn}=1$ if a Grade 3 or higher SLF is observed and $y_{ijklmn}=0$ otherwise for the n^{th} subject, from the m^{th} site, assigned to the i^{th} study lens for the j^{th} eye in the k^{th} period using the l^{th} sequence.

$$y_{ijklmn} \sim \text{Binary}(p_{ijklmn})$$

$$p_{ijklmn} = \frac{\exp(\mu_{ijklmn})}{1 + \exp(\mu_{ijklmn})}$$

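### Discontinuation at any unacceptable fit leaves later Test-lens fit records to subjects who already passed, so the >90% fit test passes too easily, by an amount that depends on Control fit and on the records counted

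*SAP*

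**What the plan says.** **Stopping rule.** The fit-assessment steps in Protocol 7.2 (Visit 1 fitting, then Visit 2 and Visit 3 follow-ups and fittings) carry the same instruction: "If the fit is graded as unacceptable based on the criteria below, then the subject is discontinued from the study", with no replacement. No step distinguishes Test from Control. The continuance steps also require acceptable fit in both eyes.

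**Endpoint.** SAP 4.1 says "Fit acceptance rate will be based on the lens fit acceptance of eyes wearing the Test lens only". The model in SAP 11.1 sets the outcome to 1 "if an acceptable lens fit is observed for eyes wearing the Test lens only". The hypothesis in SAP 5.1 reads "The proportion of eyes with acceptable fit will be greater than 90% across all visits". The decision rule in SAP 11.1 is: "Success for acceptable fit will be declared if the lower bound of the 2-sided 95% credible interval of the proportion is greater than 0.90".

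**Records.** SAP 4.1 and the time-and-event tables have fit assessed at both fitting and follow-up. SAP 8.6 imputes nothing; multiple imputation is a sensitivity analysis used only if dropout exceeds 15%.

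**Analysis set.** SAP 6.4 makes the per-protocol set (all visits completed) the primary population. SAP 6.3 sends safety analyses to the safety population. Fit is listed as a primary safety endpoint, and the SAP does not say which set applies to it.

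**Planning assumptions.** SAP 8.4 takes a 95% acceptance rate and a correlation of 0.80 within subject and period, "assuming a correlation of 0.50 between measurements within the same subject across periods".

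**The concern.** The stopping rule acts as a filter on the endpoint's own data. In Control/Test/Test, a subject whose Control lens fits badly leaves before any Test record exists, and a Test-only endpoint cannot see that removal. A subject who fails on Test in period 2 gives no period 3 record, while each subject who passes adds more successes. Both lenses share material, base curve and diameter (Protocol Table 1), so a bad fit on one plausibly predicts a bad fit on the other. The SAP's 0.50 assumes as much across periods.

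SAP 5.1 requires every primary hypothesis to be met, so each must be able to fail. The lenses come from a new manufacturing line evaluated clinically here for the first time (Protocol 1), and detecting a changed fit rate is what this test is for.

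**Working it through.** **1. The plan's own figure.** SAP Table 11 gives 65 subjects and 80% power for fit. With a true 95%, the stated correlations and subject-clustered bounds, simulated power at 65 subjects was 29–31% (logit, 2-sided 95%), 56–58% (Wald, 2-sided 95%) and 65–66% (Wald, one-sided 5%). The figure does not reproduce from its stated inputs, and the SAP does not name the test behind it. The steps below do not depend on it.

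**2. Expected rate by hand.** Inputs: true Test rate 0.90 (the null boundary), correlations 0.80 and 0.50 (SAP 8.4), and 60 subjects per sequence (120, 1:1). One record per eye per period is a simplification.

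A nested mixture meets both correlations. A subject state is good with probability 0.9. Each period copies it with probability a = √(0.50/0.80) = 0.7906, otherwise drawing afresh. Each eye copies the period state with probability b = √0.80 = 0.8944, otherwise drawing afresh.

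- Eye acceptable, period good: 0.8944 + 0.1056×0.9 = 0.9894. Period poor: 0.1056×0.9 = 0.0950.
- Period good, subject good: 0.7906 + 0.2094×0.9 = 0.9791. Subject poor: 0.2094×0.9 = 0.1885.
- Eye acceptable, subject good: 0.9791×0.9894 + 0.0209×0.0950 = 0.9707. Subject poor: 0.1885×0.9894 + 0.8115×0.0950 = 0.2636.
- Both eyes acceptable, subject good: 0.9791×0.9894² + 0.0209×0.0950² = 0.9587. Subject poor: 0.1885×0.9894² + 0.8115×0.0950² = 0.1919.

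Share still in after k periods: S_k = 0.9×0.9587^k + 0.1×0.1919^k, so S₁ = 0.8820 and S₂ = 0.8308.

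Acceptance among those left: A_k = (0.9×0.9587^k×0.9707 + 0.1×0.1919^k×0.2636)/S_k, so A₀ = 0.9000, A₁ = 0.9553 and A₂ = 0.9676.

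| Test records (60 subjects = 120 eyes per sequence) | Control also 90% | Control never fails |
|---|---|---|
| Test/Control/Control, period 1 | 120 × 0.9000 = 108.00 | 120 × 0.9000 = 108.00 |
| Control/Test/Test, period 2 | 105.84 × 0.9553 = 101.11 | 120 × 0.9000 = 108.00 |
| Control/Test/Test, period 3 | 99.70 × 0.9676 = 96.47 | 105.84 × 0.9553 = 101.11 |
| Observed rate | 305.58/325.54 = **93.9%** | 317.11/345.84 = **91.7%** |

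With zero cross-period correlation a = 0, the subject state carries no information, and the rate stays at 90%.

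**3. Pass rate by simulation.** True Test rate 90%, 120 subjects and 0.80/0.50 unless stated; lower 2-sided 95% cluster-robust bound above 0.90. Ranges span the mixture and a Gaussian copula.

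| Set-up | Observed | Passes |
|---|---|---|
| No discontinuation, Wald | 90% | about 6% |
| Control 90%, Wald | 94% | 61% (copula), 58% (mixture) |
| Control 95%, Wald | – | 44% |
| Control 98%, Wald | – | about 30% |
| Control never fails, Wald | 92% | 17–19% |
| Control 90%, logit bound | 94% | 40–42% |
| Control never fails, logit bound | 92% | 9% |
| Cross-period correlation 0.20, Control 90% | 92% | 9–20% |
| Zero cross-period correlation | 90% | 2–5% |
| Fitting and follow-up both counted, Control 90% | 95–97% | 95–100% |
| The same, Control never fails | 94–95% | 69–98% |
| Per-protocol completers, both counted | 99.8–99.9% | 100% |

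**4. First Test record only.** From the table in step 2, the expected rate is (108.00 + 101.11)/(120 + 105.84) = 92.6% if Control also fits 90%, and 90.0% if Control never fails. Simulated passing (Wald) is 28% and about 6%.

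**The case against.** Four objections carry weight.

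- **The Control assumption drives the size.** The 94% and 61% need Control to fail in 10% of eyes. SAP Table 8 shows no Control failures, and with none the pass rate is 17–19%. This stands, so 61% is one scenario among several. A reader might take it as the plan's error rate; the documents do not support that.
- **The planned analysis is a Bayesian random-effects logistic model, which was not simulated.** It sees period 2 Test failures and so partly adjusts for the lost period 3 records. A random-intercept likelihood fit, averaged over subjects, gave about 92% instead of 94%: smaller, but not removed. No model of Test records alone can recover subjects removed for Control fit. The Wald bound is also slightly liberal, passing about 6% without any discontinuation.
- **The 0.50 is a planning assumption, not an estimate.** A reader might infer that the bias always favours success. It does so under positive cross-period correlation and vanishes at zero.
- **A true rate near 90% is remote from past experience.** SAP 8.4 reports one Test failure. This lowers the urgency, but it does not make the test sound for a new production line.

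Another tempting step is to score Control failures as Test failures in the primary analysis. That contradicts the Test-only endpoint and penalises a good Test lens: at a true Test rate of 98% with Control at 90%, it would pass only about half the time.

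**Conclusion.** The selection follows from the plan as written, given the SAP's own positive correlation: the fit test compares an enriched rate with 90%. At a true 90%, with 0.80/0.50, one record per eye per period and a Wald bound, the pass rate runs from 17–19% (Control never fails) to 61% (Control also 90%), against about 6% without discontinuation and a nominal 2.5%. A logit bound or a lower correlation reduces it. Counting both scheduled assessments, or using completers only, raises it to 69–100%. Because the SAP leaves the analysis set for fit open and the Bayesian model was not simulated, no single figure can be given as the plan's own.

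Only the Visit 1 Test fitting in Test/Control/Control is free of selection. Even the Visit 2 follow-up in that sequence contains only subjects who passed the fitting. The point should be fixed, but it is not critical, since the historical studies show at most one Test failure. Nothing here suggests that the Test lens fits badly.

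**What to change.** Leave the discontinuation rule unchanged and amend SAP 4.1, 6 and 11.1:

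1. Analyse fit in the safety population, not the per-protocol set.
2. Take one primary record per eye, the result at the first Test-lens fitting: Visit 1 in Test/Control/Control, Visit 2 in Control/Test/Test.
3. Report follow-up and period 3 Test fits as supportive.
4. Show the Visit 1 fitting in Test/Control/Control alone as the unselected estimate.
5. As a sensitivity bound, not the primary rule, count Control/Test/Test subjects removed for Control fit with that observed result.
6. Shrink the fit model to match. With one record per eye, the period, sequence and carryover terms are the same contrast, so only one can stay.

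**Cost.** The data are already collected; only wording changes. There are fewer records: at most 120×2 = 240, against 60×2 + 60×4 = 360 with one per eye per period. In the same simulation (Wald bound), power is about 73–90% at a true 95% and essentially 100% at 98% or more. Selection by Control fit remains: at a true 90% the rule still passes 28% of the time if Control also fits 90%, and about 6% if Control never fails. The estimates in items 4 and 5 must therefore be read alongside the primary result.

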4.2. Secondary Endpoints

CLUE Overall Quality of Vision and Handling

Overall Quality of vision and handling scores will be assessed using the Contact Lens User Experience (CLUE)¹ questionnaire at the two-week follow-up.

Overall Quality of Vision Outdoors

Overall quality of vision outdoors will be assessed using the individual item [REDACTED] “Overall quality of vision outdoors” from the market research questionnaire. This item uses the response scale, 0: Not Applicable, 1: Excellent, 2: Very Good, 3: Good, 4: Fair and 5: Poor.

4.3. Other Endpoints

Lens Preferences

Lens preferences will be assessed by individual items regarding lens preference at the two-week follow-up of the second wearing period (Visit 3). Subjects will be asked to choose for each preference item one of the following responses: Strongly Prefer the first lens, Prefer the first lens, no preference, prefer the second lens, strongly prefer the second lens. Lens preference questions consist of:

1. Overall lens preference [REDACTED]
2. Overall comfort [REDACTED]
3. Overall vision [REDACTED]
4. Overall reduction of glare [REDACTED]

5. Overall preference indoors [REDACTED]
6. Overall preference outdoors [REDACTED]
7. Overall preference while driving during the day [REDACTED]
8. Overall preference while driving at night [REDACTED]
9. Overall preference while using computer screens & digital devices [REDACTED]
[REDACTED]

Driving Performance

Driving performance will be assessed by two individual patient reported outcomes (PRO) questions at the two-week follow-up evaluation. The individual items are as follows:

1. Reduction in glare while driving during the day [REDACTED]
2. Reduction in glare while driving during the night [REDACTED]

Indoor Performance

Indoor performance will be assessed by three individual items at the two-week follow-up evaluation. The individual items are as follows:

1. Reduction in glare from the computer screen or digital devices [REDACTED]
2. Reduction in glare caused by bright indoor lights [REDACTED]
3. Reduction in glare caused by bright light coming through the window [REDACTED]

Outdoor Performance

Outdoor performance will be assessed by four individual items at the two-week follow-up evaluation. The individual items are as follows:

1. Ability to see comfortably in bright sunlight [REDACTED]
2. Reduction in glare in bright sunlight [REDACTED]
3. Reduction in squinting in bright sunlight [REDACTED]
4. Reduction in eye strain in bright sunlight [REDACTED]

All driving, indoor and outdoor (PRO) items above will be assessed using the same excellence scale of; 0: Not Applicable, 1: Excellent, 2: Very Good, 3: Good, 4: Fair and 5: Poor.

Contrast sensitivity will also be evaluated during this study.

